Our primary goal is to test the mechanism by which AAIs reduce anxiety (**Aim 1**). There are at least two possible hypotheses for the processes underlying anxiety reduction in AAIs. First, social support is broadly associated with beneficial psychological and physiological functioning (for review, see Uchino, Cacioppo, & Kiecolt-Glaser, 1996). In particular, social support can buffer the effects of laboratory based stressors (Heinrichs et al., 2003). According to Social Baseline Theory (Coan & Sbarra, 2015), humans are inherently social, and evaluate challenges based on their ability to meet goals. Part of this implicit calculation includes social relationships (e.g. friends, family, colleagues) that might be helpful in meeting goals. One possibility is that when a person interacts with an animal, a relationship is formed that becomes part of the person's representation of social resources. For instance, being around a friendly dog might decrease the possibility of being surprised by another human or animal, thus reducing risk and decreasing anxiety. Therefore, the first mechanism we will test is whether social interaction with an animal buffers anxiety in the presence of a social stressor.

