*Experimental Procedure:* During the experimental session, participants will first be informed about the study, and if consent is given by the individual (and legal parent or guardian) they will be enrolled as a participant. To test the mechanism by which interacting with dogs can reduce anxiety, participants will be randomly assigned to one of three conditions that vary the nature of the interaction: 1) interaction with a stuffed toy dog (control condition); 2) social interaction (no physical contact) with a real dog; and 3) social + physical interaction with a real dog. We will not include a physical interaction only condition because it would be impractical to block the possibility for social interaction while allowing physical interaction. A stuffed toy dog will be used as an active control condition to control for the novelty of an animal-related stimulus.

Participants in all three conditions will listen to a therapy animal handler speak for several minutes about his or her dog and view a photo of the dog, in order to further control for the novelty effects of an animal stimulus and to provide a baseline rest period (20 minutes). During this rest period, participants will also complete the first self-report anxiety questionnaire and be fitted to the wearable heart rate device.

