In the control condition (1), participants will listen to the verbal presentation but there will be no animal present. Instead, there will be a stuffed toy dog (Beetz et al., 2012) and a person (to mirror the therapy dog handler). In both animal interaction conditions, one therapy dog and his or her handler will accompany the participant during all phases of the TSST-C. In the social interaction condition (2), participants will be told that the dog will be present, and they can socially interact with it at any point during the experiment (i.e., talking, social referencing), but they will not be permitted to touch the dog. In the social + physical interaction condition (3), participants will be told that the dog will be next to them and that they will be encouraged to interact socially and touch the dog during the experiment. Animal handlers are will be trained to provide consistently minimal verbal contact, to reduce the confounding effects of handler variability and distraction from the TSST-C tasks. All dog/handler teams will be approved through the Pet Partners animal therapy organization, and per the Pet Partners guidelines, all dogs will be on a 6' leash. To simulate a typical AAI environment, the handler will remain in proximity to the dog to monitor his/her behavior, but will not block the participant or interfere with the TSST-C tasks in any way.

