The primary task all participants will complete is the Trier Social Stress Task for Children (TSST-C), which involves six distinct phases: baseline, anticipation, preparation, speech, mental math, and recovery (Buske-Kirschbaum et al., 1997). The TSST-C (as well as the adult version of the TSST) has been used extensively as a robust and reliable method for inducing social stress, and variants have been used in conjunction with animal interaction (e.g., Allen et al., 2002; Polheber & Matchock, 2013). The TSST-C was originally validated for use in 10-14 year olds (Buske-Kirschbaum et al., 1997), but the protocol used in this study is a specific adaptation validated for use in adolescents up to 17 years old (Stroud et al., 2009). The TSST-C involves a public speaking task and a mental arithmetic performance challenge. During the baseline rest period (20 minutes) rest period, participants will watch a science documentary (with no animal content) on a digital tablet. Participants will then be told about the task (anticipation). Then participants will have a 5-minute preparation period, and then they will be asked to speak on an academic topic for 5 minutes (e.g., give a plot summary and interpretation of a book of their choice). They will then be asked to complete a serial subtraction mental arithmetic task for 5 minutes. Per the Stroud et al. (2009) protocol, the serial subtraction task will be adjusted for age (13-14 year olds will subtract by 11s, 15-17 year olds will subtract by 17s). If an error is made, participants will be instructed to restart from the beginning.

Finally, there will be a 30-minute recovery period where they will continue to watch the science documentary. Throughout the TSST-C, participants will be asked to self-report their anxiety levels at each of the 6 phases and will wear a watch-like wristband (Empatica E4) to continuously measure heart rate data.

Compensation for the screening process will be a \$10 gift card (duration approximately 10 minutes). Youth who meet the eligibility criteria and who participate in the experiment will be compensated with a \$75 gift card (duration of the study approximately 2 hours, not including travel time to Tufts University).

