## Measures

To test the mechanism of action for canine interaction in reducing social anxiety in adolescents, we will collect three levels of outcome data: a) self-reported experience (anxiety), b) autonomic physiological reactivity (heart rate), and c) cognitive performance (error rates on mental math task).

*Social anxiety.* The SAS-A will be used to assess overall level of social anxiety. The SAS-A was designed for use in adolescence and has been validated extensively across many samples and in multiple languages (e.g., Garcia-Lopez et al., 2011; La Greca & Lopez, 1998). The SAS-A contains 18 items that include three domains of social anxiety: fear of negative evaluation from peers, social avoidance and distress in new situations, and generalized social avoidance.

*Self-Report Experience:* Self-reported affective experience will be measured using the state scale of the State-Trait Anxiety Inventory (STAI; Spielberger et al., 1983), which is validated for use in adolescence and is commonly used with the TSST. The STAI state scale contains 20-items rated on a four-point scale, and has consistently demonstrated excellent reliability (ranging from  $\alpha = .86$  to  $.95$ ; Spielberger et al., 1983) and construct validity (Spielberger, 1989). Anxiety will be measured at six time points, during: (1) baseline, (2) anticipation (3) preparation, (4) speech, (5) mental math, and (6) recovery.

*Autonomic physiological reactivity:* Heart rate and electrodermal activity will be collected continuously using a clinical grade wristband sensor (Empatica E4; Garbarino et al., 2015).

*Cognitive Performance:* Cognitive performance during the social stressor task will be measured to understand how anxiety and AAI influence cognitive function. As recommended by existing research with the TSST paradigm (e.g., Simeon et al., 2007), we will measure cognitive performance during the mental arithmetic task by tracking the number of errors and lowest number reached by participants on the mental math task. Better performance will be characterized by fewer errors and reaching a lower number during serial subtraction.

*Demographic Characteristics:* In addition to the measures assessing the primary aims, we will also collect demographic covariate information from participants on age, sex, race/ethnicity, and current pet ownership.

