### *Analyses:*

To test our confirmatory hypotheses, we conducted two three-way analyses of variance (ANOVA) with either self-reported anxiety (STAI), autonomic reactivity (electrodermal activity [EDA] and heart rate [HR]) as the dependent variable. For these outcomes, there were two between-subjects factors, condition (social, social + physical, control) and social anxiety (SA; centered continuous predictor), and one within-subjects factor, time point (1, 2, 3, 4, 5, 6). We included baseline STAI, EDA, or HR at time point 1 as a centered continuous covariate. For cognitive performance, we conducted ANOVAs that treated condition as a between-subjects categorical factor and social anxiety as a centered continuous predictor.

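### Time point 1 is both a repeated outcome level and the baseline covariate, so the phase-averaged dog effect is 5/6 of the post-baseline effect and the condition-by-time test cannot show differences among stressor phases

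*SAP*

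**What the plan says.** The Analyses section of the SAP specifies, for STAI, EDA and HR, an ANOVA whose between-participant terms are "condition (social, social + physical, control) and social anxiety (SA; centered continuous predictor". The repeated part of the model is "one within-subjects factor, time point (1, 2, 3, 4, 5, 6". The next sentence adds: "We included baseline STAI, EDA, or HR at time point 1 as a centered continuous covariate".

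The protocol's Measures section defines the six points for the STAI: "Anxiety will be measured at six time points, during: (1) baseline, (2) anticipation (3) preparation, (4) speech, (5) mental math, and (6) recovery". Time point 1 is thus the resting baseline, and points 2 to 6 are the later phases.

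Neither document limits the outcome to points 2 to 6, names a contrast among phases, mentions a covariate-by-time term, or says which estimate of the condition effect will be reported. Aim 1, in the protocol's Background, is to test "whether social interaction with an animal buffers anxiety in the presence of a social stressor".

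**The concern.** A measurement used as a covariate is held fixed across conditions by the model. If it is also an outcome level, that level has an adjusted condition difference of zero by construction and dilutes any average that includes it. The average would then understate the effect under stress, which is what Aim 1 asks about, in bpm, EDA units and STAI points.

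A second consequence comes from having baseline among the levels, with or without the covariate. If the dog lowers anxiety by the same amount in every later phase, the condition difference still moves from zero at time 1 to that amount afterwards. The omnibus condition-by-time test responds to this step. A reader could take a significant result as evidence that the dog helps more in, say, the speech than in recovery, when the data show only that an effect exists after baseline. In a trial about mechanism, that is a consequential misreading.

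**Working it through.** **Inputs.** From the SAP's sample size section: 25 per arm, three arms, HR SD 12 bpm, alpha 0.05, planning differences of 12 bpm and 10 STAI points (SD 10.5). Assumed, because the documents give no values: correlation between phases of 0.3, 0.5 or 0.7, equal for all pairs of phases; complete data; no dog effect at time 1.

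**The plan's own figures.** A two-sided two-sample t-test for 12 bpm with SD 12 has power 0.8997 at 22 per group and 0.9125 at 23, so the stated 23 reproduces. For 10 STAI points with SD 10.5 and 25 per group, power is 0.910, so the stated 90% also reproduces.

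**Part 1: the averaged effect.** Let b be the time 1 value and M the mean of phases 2 to 6.

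- Six-phase mean = (b + 5M)/6 = b/6 + (5/6)M.
- The between-subjects part of the model regresses this mean on condition, social anxiety, their product and b. Regressing b on a set that contains b gives condition coefficients of 0.
- Hence the condition coefficient for the six-phase mean = 0/6 + (5/6) × (condition coefficient for M). The same holds for condition by social anxiety.
- 12 bpm × 5/6 = 10 bpm; 6 × 5/6 = 5 bpm; 10 STAI points × 5/6 = 8.33. The reduction is 1/6 = 16.7%.
- The residual scales by 5/6 as well, so F and p are identical. In simulation the ratio was 0.8333 in every run, and F for condition and for condition by social anxiety agreed to within 1e-8 in relative terms. It would be wrong to infer a loss of power. Contrasts at a single phase are not scaled.

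**Part 2: the condition-by-time test.** Suppose the effect is 0 at time 1 and d at each of phases 2 to 6.

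- Its six-level mean is 5d/6. The deviations from that mean are -5d/6 at time 1 and d/6 at each later phase. Their sum of squares is (25/36 + 5/36)d² = (5/6)d², which is not zero.
- Over levels 2 to 6 alone, every deviation is 0.

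Without a covariate, the noncentrality of the six-level test is 25 × (sum of squared arm deviations) × (5/6) / [144 × (1 - correlation)]. For arm effects 0/-6/-12 the arm deviations are 6, 0 and -6, with sum of squares 72. This gives 1500/[144 × (1 - correlation)] = 14.9, 20.8 and 34.7. With 10 and 345 degrees of freedom, the rejection rates are about 74, 90 and 99%. The simulated rates below are the same or slightly lower; the fitted models also carry condition by social anxiety.

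Simulated rejection of condition by time, 4,000 trials per cell, uncorrected F, at correlation 0.3/0.5/0.7:

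| Effect constant over phases 2-6 (control / social / social + physical) | Six levels, time 1 covariate with covariate-by-time | Six levels, no covariate | Levels 2-6 only |
|---|---|---|---|
| 0/-3/-6 bpm | 20/27/47% | 20/26/43% | 4-6% |
| 0/-6/-12 bpm | 85/94/99.8% | 72/88/99.3% | 5% |
| none | 4-6% | 4-6% | 4-6% |

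A Greenhouse-Geisser correction lowers these by 0 to 3 points. A separate simulation with 12 bpm in one arm only gave 96 to 100% with covariate-by-time and 86 to 99.9% without it, against 4 to 6% for levels 2 to 6. With covariate-by-time included, the six-level multivariate interaction test is algebraically the joint test that all condition effects at times 2 to 6 are zero (same Wilks lambda, for example 0.8789 for both). It therefore tests for any post-baseline effect.

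**Timing of time 1.** The protocol's Participants and Procedure section describes a rest period with a handler's talk and a photo of the dog, and says: "During this rest period, participants will also complete the first self-report anxiety questionnaire". The same section says "one therapy dog and his or her handler will accompany the participant during all phases of the TSST-C" and describes the task as one "which involves six distinct phases: baseline, anticipation, preparation, speech, mental math, and recovery". On that reading the dog could be present at time 1. If its full effect were already there, adjusting for time 1 would leave only (1 - correlation) of it even with levels 2 to 6: 12 × 0.7/0.5/0.3 = 8.4/6.0/3.6 bpm.

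**The case against.** The strongest reply is that no hypothesis test for either aim changes. F, p and power for condition and for condition by social anxiety are identical, and the SAP does not commit to reporting the six-phase average. The 5/6 matters only if that average is reported, and a reader who knows of it can undo it. This is correct and limits the seriousness of the point. It does not remove it, because the SAP names no other estimate and the six-phase average is the one its model yields.

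Second, no aim asks whether the effect differs among phases, and the six-level interaction is a true baseline-versus-later contrast with correct type I error. That also stands: the risk is one of interpretation. But the SAP includes the time factor, names no contrast to go with it, and so leaves the interaction open to the wrong reading.

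Third, the part 2 rates depend on assumed correlations and effect patterns and on no dog effect at time 1. If the effect were equal in all six phases and no covariate-by-time term were fitted, the six-level test would reject in only 3.9 to 5.2% of trials. This stands as a condition on the figures, and it is a further reason to settle when time 1 is recorded.

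Finally, the SAP is written in the past tense. If the analyses have already been run, the change is a re-analysis and should be labelled as one.

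**Conclusion.** The concern holds and should be fixed; it does not threaten the tests of Aims 1 and 2. The 5/6 factor (-16.7%) follows from the SAP's wording and is exact for complete data, whatever the correlation and with or without a covariate-by-time term. With missing phases it becomes approximate. That the six-level interaction responds to a constant post-baseline effect is also certain. How often it does so depends on the assumed correlations and effect sizes: 20 to 47% for 0/-3/-6 bpm and 85 to 99.8% for 0/-6/-12 bpm, against about 5% when time 1 is not an outcome level. These rates assume that the dog has no effect at time 1, which the protocol leaves unclear.

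**What to change.** 1. First reconcile the protocol's statements on the rest period, the dog's presence and the baseline phase, and state in the SAP when time 1 is recorded relative to the dog's entry. The use of time 1 as a covariate depends on its preceding exposure.
2. If it does, restrict the within-subjects factor to time points 2 to 6, keep time 1 as covariate only, and add a baseline-by-time term.
3. If all six levels are kept instead, drop the covariate, specify contrasts against time 1, and add a separate test of condition by time within phases 2 to 6. Dropping the covariate alone is not enough: the largest fall in the table is from 85 to 72%.
4. State which estimate is reported: phase-specific effects or the mean of phases 2 to 6.

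The cost is SAP wording and one re-specified model per outcome. No new data and no change in sample size are needed.
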